## 5) Status of administration of concomitant drugs

## ① Use of drugs for JIA

Presence/absence of concomitant drug use for JIA, names of drugs, routes, doses, and durations

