#### 9.14. Level of significance

In principle, the significance level of statistical analyses used in this survey is two-sided 5%.  $p < 0.05$  ( $< 5\%$ ) should be considered significant.

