Previous medication (biological product): tocilizumab	“With previous medication (biological product): tocilizumab” should be selected when the drug meets the conditions of “previous medications (biological products)” and the higher order 7 digits of the drug code of the previous medication (biological product) are “6399421”, “unknown/unspecified” should be selected when the history of treatment with previous medications (biological products) is “unknown/unspecified”, and “without previous medication (biological product): tocilizumab” should be selected otherwise.
Previous medication (biological product): etanercept	“With previous medication (biological product): etanercept” should be selected when the drug meets the conditions of “previous medications (biological products)” and the higher order 7 digits of the drug code of the previous medication (biological product) are “3999424”, “unknown/unspecified” should be selected when the history of treatment with previous medications (biological products) is “unknown/unspecified”, and “without previous medication (biological product): etanercept” should be selected otherwise.
Previous medication (biological product): other	“With previous medication (biological product): other” should be selected when the drug meets the conditions of “previous medications (biological products)” and the higher order 7 digits of the drug code of the previous medication (biological product) are other than “6399421” and “3999424” and the drug falls under “Biological products” in “Drug code list_20171012.xlsx”, “unknown/unspecified” should be selected when the history of treatment with previous medications (biological products) is “unknown/unspecified”, and “without previous medication (biological product): other” should be selected otherwise.
Concomitant drugs	Concomitant drugs are defined as drugs listed in “5. Previous medications for juvenile idiopathic arthritis”, “6. Status of

Name of data	Derivation and calculation methods
	administration of concomitant drugs (1) [Concomitant drugs for juvenile idiopathic arthritis]”, “6. Status of administration of concomitant drugs (2) [Other concomitant drugs]” in the CRF and confirmed to have been administered between the start date of Humira treatment and the end date of Humira treatment.

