Name of data	Derivation and calculation methods
	
body surface area should be calculated.
 $S = W^{0.425} \times H^{0.725} \times 71.84$ 
S = body surface area (cm^2); W = body weight from the start date of Humira treatment - 28 days to the start date of Humira treatment (kg); H = height from the start date of Humira treatment - 28 days to the start date of Humira treatment (cm)
 
If the dose of methotrexate was changed during the survey period, calculate doses per body surface area for each record and calculate the mean value.

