Priority survey item	Infection, tuberculosis, interstitial pneumonia, malignant tumour, congestive cardiac failure, autoimmune disease, pancytopenia, demyelinating disease, administration site reaction
Status of previous medication: biological products	No, yes, unknown/unspecified
Status of previous medication: MTX	No, yes, unknown/unspecified
Status of previous medication: corticosteroid	No, yes, unknown/unspecified
Status of previous medication: NSAIDs	No, yes, unknown/unspecified
Status of previous medication: Other DMARDs	No, yes, unknown/unspecified
Status of concomitant drug: MTX	No, yes, unknown/unspecified
Status of MTX: details	<4 mg/m  /week, ≥4 mg/m  /week and <7 mg/m  /week, ≥7 mg/m  /week

Data	Layer separation
	and <10 mg/m  /week, ≥10 mg/m  /week, dose per body surface area unknown
Status of concomitant drug: corticosteroid	No, yes, unknown/unspecified
Status of concomitant drug: NSAIDs	No, yes, unknown/unspecified
Status of concomitant drug: Other DMARDs	No, yes, unknown/unspecified
Combination therapy for juvenile idiopathic arthritis	No, yes, unknown/unspecified
Combination therapy for juvenile idiopathic arthritis: details	Rehabilitation, other, unknown/undescribed
Duration of combination use of MTX for juvenile idiopathic arthritis	No, yes, unknown/unspecified
Duration of combination use of MTX for juvenile idiopathic arthritis: details	After the start of Humira treatment up to the end date of Humira treatment, at least a dose used during Humira treatment, unknown/unspecified
Timing of onset of adverse events	From the start of treatment and within 4 weeks of treatment, after Week 4 of treatment and within 8 weeks of treatment, after Week 8 of treatment and within 12 weeks of treatment, after Week 12 of treatment and within 16 weeks of treatment, after Week 16 of treatment and within 20 weeks of treatment, after Week 20 of treatment and within 24 weeks of treatment, after Week 24 of treatment

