Purpose of analysis: Involving adverse reactions during the safety analysis period, the number of patients and the number and percentage of patients who experienced adverse reactions will be calculated in accordance with “11. Data-layer separation” (age 1, age 2, age 3, sex, body weight, BMI, reason for use and type of disease, disease duration 2, complications, complication: liver disorder, complication: renal disorder, complication: cardiovascular disorder, complication: blood disorder, complication: respiratory disorder, complication: other, past medical history, history of allergy, Steinbrocker Staging System, Steinbrocker Functional Classification, administration method category, previous medications, status of previous medication: biological product, status of previous medication: MTX, status of previous medication: corticosteroid, status of previous medication: NSAIDs, status of previous medication: Other DMARDs, concomitant drugs, status of concomitant drug: MTX, status of MTX: details, status of concomitant drug: corticosteroid, status of concomitant drug: NSAIDs, status of concomitant drug: Other DMARDs).

For the incidence rates of adverse reactions, Fisher's exact test should be conducted when the background factor is a nominal scale and Mann-Whitney U test should be conducted when the background factor is an ordinal scale.

Notes: • Reason for use and type of disease may be redundantly aggregated. No test will be conducted for this item.

“Table 2.5.2 Incidence of adverse events in patients switched to other biological products”

Analysis object: Patients included in the safety analysis set

Purpose of analysis: Involving adverse events during the safety analysis period, the number of patients, the number and percentage of patients who experienced adverse events will be calculated on the basis of the number of patients switched to

other biological products and the breakdown of the reasons for switching (remission, subtherapeutic response, onset of adverse events, patient's request, no hospital visit [including hospital transfer], other).

Notes:

- The breakdown of the reasons for switching may be redundantly aggregated.
- “Onset of an adverse event” should apply only when “Onset of an adverse event” is selected and an adverse event during safety analysis period has occurred.

“Table 2.5.3 Incidence of adverse reactions to combination therapy for juvenile idiopathic arthritis”

Analysis object: Patients included in the safety analysis set

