Purpose of analysis: Involving adverse reactions during the safety analysis period, the number of patients, the number and the percentage of patients who experienced adverse reactions will be calculated on the basis of combination therapy for juvenile idiopathic arthritis (no, yes, unknown/unspecified). For patients receiving combination therapy, the number of patients, the number and percentage of patients who experienced adverse reactions by breakdown of combination therapy (rehabilitation, other, unknown/unspecified) will be calculated.

Notes: The breakdown of combination therapy may be redundantly aggregated.

“Table 2.5.4 Incidence of adverse reactions by duration of combination use of MTX for juvenile idiopathic arthritis”

Analysis object: Patients included in the safety analysis set

Purpose of analysis: Involving adverse reactions during the safety analysis period, the number of patients, the number and the percentage of patients who experienced adverse reactions will be calculated on the basis of duration of combination use of MTX for juvenile idiopathic arthritis (no, yes, unknown/unspecified). Where there is a duration of combination use of MTX, the number of patients, the number and percentage of patients who experienced adverse reactions by breakdown of duration of combination use (after the start of Humira treatment up to the end date of Humira treatment, at least a dose used during Humira treatment, unknown/unspecified) will be calculated.

Notes: The breakdown of duration of combination use may be redundantly aggregated.

“Table 2.5.5.X Examination of factors affecting the occurrence of adverse reactions”

Analysis object: Patients included in the safety analysis set

Purpose of analysis: For factors with a significant difference ( $p < 0.05$ ) in “Table 2.5.1”, adverse reactions during the safety analysis period will be aggregated by stratification factor as shown below. The number of patients analyzed, the number and percentage of patients who experienced adverse reactions, the number of adverse reactions, the number of patients who experienced adverse reactions by type of adverse reaction (by SOC and PT) and their percentages against the patients analyzed will be calculated.

Number of patients who experienced adverse reactions (or serious adverse

reactions): Number of patients who experienced adverse reactions (or serious adverse reactions).

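### Methotrexate dose per body surface area is averaged equally over records when the dose changed, so some patients with records of unequal length can fall in the wrong dose class

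*SAP*

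**What the plan says.** SAP 10.1 (dose of concomitant drug methotrexate per body surface area) computes one body surface area per patient from height and weight in the 28 days up to Humira start. If the methotrexate dose changed during the survey period, the analyst must "calculate doses per body surface area for each record and calculate the mean value". Neither days nor number of doses enters as a weight.

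The records come from the SAP 10.1 definition of concomitant drugs. It draws on the CRF sections for previous medication and for concomitant drugs, and requires only that the drug be "confirmed to have been administered between the start date of Humira treatment and the end date of Humira treatment". No minimum overlap is stated.

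SAP 11 sorts the value into <4, 4 to <7, 7 to <10 and >=10 mg/m2/week, plus "dose per body surface area unknown". The class enters Tables 2.5.1, 3.1 and 3.5.2 as a background factor ("status of concomitant drug: MTX, status of MTX: details") and forms the strata of Table 2.11. The dose is also described in Table 1.3. For factors on an ordered scale, Table 2.5.1 says "Mann-Whitney U test should be conducted when the background factor is an ordinal scale", and SAP 9.14 sets a two-sided 5% level. The instruction for Table 2.5.5.X opens "For factors with a significant difference" and adds a further breakdown of adverse reactions for those factors.

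The data for weighting are planned: Protocol 8 (3) 5) ① lists "Presence/absence of concomitant drug use for JIA, names of drugs, routes, doses, and durations", and SAP Table 4.3.4 lists start and end dates for each concomitant drug.

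**The concern.** The classes are expressed as a weekly dose, so a reader will take them to describe exposure. A plain mean over records measures exposure only when the records are equally long. Otherwise a short record counts as much as a long one, and a record that overlaps Humira treatment by a single day counts in full.

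The value also depends on data entry. If one dosing period is written as two rows, the mean changes although the exposure does not.

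The same SAP section handles the Humira mean dose differently. There, total dose is divided by total number of doses, so longer periods count for more. No reason is given for the different treatment of methotrexate.

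At stake is the relation between methotrexate dose and adverse reactions, remission and EULAR response. Factors affecting safety and efficacy are a stated purpose of the survey (Protocol 1, SAP 4.1). With a target of 100 patients spread over several classes, moving a few patients could alter small cells.

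**Working it through.** The documents give no figure for this derivation, so there is none to reproduce. The check compares two means and the class each one assigns.

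**Inputs from the documents.** Averaging rule and body surface area formula: SAP 10.1. Class cuts at 4, 7 and 10 mg/m2/week: SAP 11. Observation of 24 weeks, or 168 days: Protocol 8 (1), SAP 10.1.

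**Assumed inputs.** All methotrexate doses and durations, and a patient of 30 kg and 135 cm.

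**Formulas.** For records with dose d (mg/m2/week) and length t:

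- SAP mean = sum(d) / number of records
- Time-weighted mean = sum(d x t) / sum(t)

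For two records, a for t1 days and then b for the rest of T days, SAP mean minus weighted mean = (a - b) x (1/2 - t1/T). This is zero when the lengths are equal, and its sign depends on whether the shorter record has the higher or the lower dose.

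**Doses given directly in mg/m2/week, over 24 weeks**

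- 2 weeks at 2, then 22 weeks at 10: SAP (2 + 10)/2 = 6.0, class 4 to <7. Weighted (2x2 + 22x10)/24 = 224/24 = 9.33, class 7 to <10.
- 2 weeks at 2, then 22 weeks at 11: SAP 6.5, class 4 to <7. Weighted 246/24 = 10.25, class >=10, two classes apart.
- Reverse direction, 2 weeks at 10, then 22 weeks at 2: SAP 6.0, class 4 to <7. Weighted (20 + 44)/24 = 2.67, class <4.

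**Smaller steps.** Body surface area = 30^0.425 x 135^0.725 x 71.84 / 10,000 = 1.068 m2. The same area applies to every record of a patient, so only dose and time matter.

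| Records (mg/week, days) | SAP mean | Weighted mean | Class |
|---|---|---|---|
| 6 for 28, 8 for 140 | (5.62 + 7.49)/2 = 6.55 | (6x28 + 8x140)/168/1.068 = 7.18 | differs (cut at 7) |
| 4 for 14, 8 for 154 | 5.62 | 7.18 | differs (cut at 7) |
| 4 for 28, 10 for 140 | 6.55 | 8.43 | differs (cut at 7) |
| 6 for 28, 10 for 140 | 7.49 | 8.74 | same |
| 8 for 84, 10 for 84 | 8.43 | 8.43 | same |

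**Dependence on rows.** Rows of 5 and 8.5 mg/m2/week give 6.75, class 4 to <7. With the second period written as two rows, the mean is (5 + 8.5 + 8.5)/3 = 7.33, class 7 to <10.

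**Range.** Over all unequal dose pairs from 2 to 15 mg/m2/week in steps of 0.25, the share of pairs whose class differs depends on the length of the first record:

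| First record (days of 168) | 1 | 14 | 28 | 42 | 56 | 84 |
|---|---|---|---|---|---|---|
| Pairs with a different class | 52% | 50% | 43% | 34% | 23% | 0% |

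The grid gives every dose pair the same weight. It shows how sensitive the rule is to record length and does not estimate how many patients are affected.

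**The case against.** The strongest objection is that weighting over the whole Humira period is not better everywhere. Take 2 weeks at 10 mg/m2/week, an adverse reaction, then 22 weeks at 2. The dose at the reaction was in class >=10. The SAP mean is 6.0 and the weighted mean 2.67, so full-period weighting moves the patient further from the dose at the event and lets later dosing set the class. This stands, and it is why the adverse reaction tables need a different window.

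Second, day weights need complete dates. SAP 9.2 treats a partial date as unknown, SAP 9.1 bars imputation unless an item defines it, and SAP 9.3 drops unknowns from tests. Without a fallback, weighting would lose patients. This also stands.

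Third, the reach is limited. The methotrexate class is one of 32 factors listed for Table 2.5.1, and a significant result only leads to a further breakdown. Table 2.11 is descriptive. Whether methotrexate was used at all is analysed separately and is unaffected. The SAP never labels the class as ordinal, so its testing by Mann-Whitney U is an inference from the ordered cuts. All of this limits the weight of the point without removing it.

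Two stronger readings are tempting. A reader might infer that patients with a dose change generally land in the wrong class. The documents do not support that, because unequal lengths and a cut between the two means are also needed. A reader might also infer that the misplaced patients are mainly those whose methotrexate was changed for toxicity or lack of effect. The protocol lists reasons for changes in the Humira dose, but none for changes in methotrexate, so nothing supports it.

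**Conclusion.** The point holds in a limited form. Followed as written, SAP 10.1 does not give an average weekly methotrexate dose when records differ in length, and its result depends on how many rows were entered. Some patients can therefore fall in the wrong class in Tables 2.5.1, 2.11, 3.1 and 3.5.2. In the assumed examples the shift is zero, one or two classes, and it can go up or down.

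This rests on reading the mean as unweighted, which is the plain reading although the SAP does not use that word, and on taking average weekly exposure as what the mg/m2/week classes are meant to show. The number of patients affected cannot be derived from the documents. The overall adverse reaction incidence and the comparison of patients with and without methotrexate do not depend on this rule.

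This is a flaw in how a variable is defined, not a miscalculated figure. It is worth correcting because the better rule uses data already collected.

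**What to change.** In SAP 10.1, replace the mean over records as follows.

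- **Tables 1.3, 3.1 and 3.5.2:** use sum(dose per m2 x days) / sum(days), counting only days on which a methotrexate record overlaps Humira treatment.
- **Tables 2.5.1 and 2.11:** count only days up to the first adverse reaction, or use the methotrexate dose at Humira start. Either choice stops dosing after the event from setting the class. The first compares different time windows in patients with and without a reaction; the second avoids this but ignores later changes. Choose one and state it.
- **Incomplete record dates:** keep the present mean over records and footnote the number of such patients.

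The text should also say how overlapping records are handled, and how to class a patient with no methotrexate days in the window. If weighting was already intended, the text should say so and add the window for the safety tables.

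The cost is a few lines of SAP text, a little more programming, and a fallback group whose size the footnote will show. No new data are needed.

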#### 10.2. Safety analysis

Name of data	Derivation and calculation methods
Adverse events	
For adverse event-related data, “an AE matching list”, the data set through the AE matching activities (matching of CRF data and safety information data), should be used.
 
Adverse events with the same case number should be counted as one event when the PT is the same.
 
See the definition document for analytical dataset as aggregation of adverse events is conducted at the time of the creation of analytical dataset.
 
Name of analytical dataset: A_AE Name of variable: AETERM

Seriousness of adverse events	
For seriousness of adverse events aggravated from a single patient as the same PT, seriousness of the company-determined CRF data set through the AE matching activities should be set in the following order of priority:
 
(1) Serious (2) Non-serious
 
See the definition document for analytical dataset as setting of seriousness of adverse events is conducted at the time of the creation of analytical dataset.
 
Name of analytical dataset: A_AE_AL Name of variable: AESERS

Causal relationship of adverse events	
Where the causal relationship set through AE matching is other than “not related”, the causal relationship is defined as related. For causal relationship of an adverse event aggravated from a single patient as the same PT, causal relationship set through AE matching activities should be set in the following order of priority:
 
(2) Related (2) Not related
 
See the definition document for analytical dataset as setting of causal relationship of adverse events is conducted at the time of the creation of analytical dataset.
 
Name of analytical dataset: A_AE_AL

Name of data	Derivation and calculation methods
Outcomes of adverse events	
Name of variable: AERELS
 
Outcomes of adverse events aggravated from a single patient as the same PT should be set in the following order of priority:
 
(1) Fatal (2) Unknown (3) Not recovered/not resolved (4) Recovered/resolved with sequelae (5) Recovering/resolving (6) Recovered/resolved (7) Unspecified
 
See the definition document for analytical dataset as setting of outcomes of adverse events is conducted at the time of the creation of analytical dataset.
 
Name of analytical dataset: A_AE_AL
 
Name of variable: AEOUTS

Timing of onset of adverse events	
With the start date of treatment as Day 1
 
Adverse events that occurred after the start of treatment and within 4 weeks of treatment (Days 1 to 28)
 
Adverse events that occurred after Week 4 of treatment and within 8 weeks of treatment (Days 29 to 56)
 
Adverse events that occurred after Week 8 of treatment and within 12 weeks of treatment (Days 57 to 84)
 
Adverse events that occurred after Week 12 of treatment and within 16 weeks of treatment (Days 85 to 112)
 
Adverse events that occurred after Week 16 of treatment and within 20 weeks of treatment (Days 113 to 140)
 
Adverse events that occurred after Week 20 of treatment and within 24 weeks of treatment (Days 141 to 168)
 
Occurrence of adverse events after the end of treatment: Adverse events that occurred at and after Week 24 of treatment (on and after Day 169)

Adverse events occurred during treatment	Adverse events that occurred after the start date of Humira treatment by the end date or the date of discontinuation of Humira treatment
Adverse events occurred after treatment	Adverse events that occurred after the end date or the date of discontinuation of Humira treatment by the start date of Humira treatment + 196 days
Serious adverse events	Adverse events whose seriousness set through the AE matching activities is “serious” are defined as serious adverse events.
Adverse reactions	
Adverse events whose causal relationship is other than “not related” based on company-determined data set through the AE matching activities are defined as adverse reactions.
 
Adverse reactions with the same case number should be counted as one event when the PT is the same.
 
Name of analytical dataset: A_AE_AL
 
Names of variables: AERELS, AESOCCD, AEPTCD

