## 2. Definition of terms and abbreviations

The terms and abbreviations used in this statistical analysis plan are defined as follows.

Terms and abbreviations	Definition
Adverse events	An adverse event refers to any unfavorable and unintended sign (including an abnormal laboratory finding), symptom or disease associated with the use of a drug, whether or not considered related to the drug.
Adverse events during the safety analysis period	Adverse events that occurred during the period up to the start date of Humira treatment + 196 days.
Adverse events outside the safety analysis period	Adverse events that occurred prior to the start date of Humira treatment or after the start date of Humira treatment + 196 days.
Adverse reactions	Of adverse events, events for which causal relationship with Humira cannot be ruled out are defined as adverse reactions.
Adverse reactions during the safety analysis period	Of adverse events during safety analysis period, events for which a causal relationship with Humira cannot be ruled out are defined as adverse reactions during safety analysis period.
Adverse reactions outside the safety analysis period	Of adverse events outside safety analysis period, events for which a causal relationship with Humira cannot be ruled out are defined as adverse reactions outside the safety analysis period.
Basic statistics	Basic statistics include sample size, mean value, standard deviation, minimum value, median value, maximum value, first quartile and third quartile.
MedDRA/J	Medical Dictionary for Regulatory Activities/Japanese edition
SOC	MedDRA/J System Organ Class
PT	MedDRA/J Preferred Term
CDAI	Clinical Disease Activity Index
CRP	C-Reactive Protein
DAS	Disease Activity Score
DMARDs	Disease Modifying Antirheumatic Drugs
EULAR	European League Against Rheumatism
ESR	Erythrocyte Sedimentation Rate
JIA	Juvenile idiopathic arthritis
MTX	Methotrexate
NSAIDs	Non-Steroidal Anti-Inflammatory Drugs
SDAI	Simplified Disease Activity Index
VAS	Visual Analog Scale

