#### “Table 2.2 Appended Form 10”

Analysis object: Patients included in the safety analysis set

Purpose of analysis: Involving adverse events during the safety analysis period, the following items will be aggregated by period.

Number of investigating facilities: Number of facilities included in the survey.

When multiple clinical departments in a single facility have been contracted, they should be counted as one facility.

Number of patients surveyed: Number of patients included in the safety analysis set.

Number of patients who experienced events: Number of patients who

experienced serious adverse events.

Number of cases: Number of serious adverse events that occurred. When a single patient experienced multiple episodes of the same serious adverse event (PT), they should be counted as one event.

Percentage of patients who experienced events: Number of patients who experienced serious adverse events ÷ number of patients included in the safety analysis set x 100.

Types of serious adverse events: Should be calculated by SOC and by PT. Output data should be sorted in the order of international agreements and in the ascending PT code order. When a single patient experienced multiple episodes of the same serious adverse event (PT), they should be counted as one event.

Notes:

- The categories of period should be status up to approval, drug use-results survey, special drug use-results survey, post-marketing clinical study, and total.
- The version of MedDRA/J used should be provided.
- Adverse events that cannot be expected from “Precautions” in the package insert should be indicated with \*.
- The number of events for which the causal relationship was ruled out should be shown in [ ].

“Table 2.3 List of incidence of adverse reactions in this survey”

Analysis object: Patients included in the safety analysis set

Purpose of analysis: Adverse reactions or serious adverse reactions during the safety analysis period will be aggregated as follows.

Number of patients surveyed: Number of patients included in the safety analysis set.

Number of patients who experienced adverse reactions (or serious adverse reactions): Number of patients who experienced adverse reactions (or serious adverse reactions).

Number of adverse reactions (or serious adverse reactions): Number of adverse reactions (or serious adverse reactions) that occurred. When a single patient experienced multiple episodes of the same adverse reaction (PT), they should be counted as one event.

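### Does merging same-PT episodes on seriousness and causality separately create false serious adverse reactions?

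*SAP*

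**What the plan says.** SAP section 10.2 treats repeat episodes of one PT in one patient as one event and gives the merged record its attributes one at a time.

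- **Seriousness (AESERS).** "For seriousness of adverse events aggravated from a single patient as the same PT, seriousness of the company-determined CRF data set" is ranked with serious ahead of non-serious.
- **Causality (AERELS).** "For causal relationship of an adverse event aggravated from a single patient as the same PT, causal relationship set through AE matching activities" is ranked with related listed ahead of not related. Both options carry the number 2, a clerical slip; the listing order and the parallel with seriousness make the intent clear. In both rows the word for combining episodes is evidently meant as 'aggregated'.
- **Where the detail sits.** "See the definition document for analytical dataset as setting of causal relationship of adverse events is conducted at the time of the creation" of the analytical dataset. The seriousness and outcome rows carry the same kind of reference.
- **Adverse reactions.** These are events whose company-determined causality from AE matching is anything but unrelated. The row adds "Adverse reactions with the same case number should be counted as one event when the PT is the same" and ends "Names of variables: AERELS, AESOCCD, AEPTCD". Section 2 defines the term at event level: "events for which causal relationship with Humira cannot be ruled out are defined as adverse reactions".

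Neither section 2 nor section 10.2 has an entry for a serious adverse reaction. The term is used in Table 2.3 ("Adverse reactions or serious adverse reactions during the safety analysis period will be aggregated as follows") and in Table 2.14, and is implied where Table 2.4 splits adverse reactions by seriousness. For serious adverse events, Table 2.2 notes "The number of events for which the causal relationship was ruled out should be shown in" square brackets.

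**The concern.** Two worst-case rules applied separately can combine attributes of different episodes. Suppose a patient has a serious infection judged unrelated and later a mild infection, coded to the same PT, judged related. The merged record is serious and related. Read straight from that record, the patient has a serious adverse reaction that no physician or company assessment ever described. In Table 2.2 the serious event would also no longer be bracketed as having causality ruled out.

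The survey's first aim stresses clinically significant reactions, and the results go to the authority and into the reexamination file (SAP sections 3.1 and 4.1). In a set of 100 patients, one such record adds 1 percentage point to the serious adverse reaction rate if the patient has no genuine one. Two programmers working from the SAP alone might also report different counts.

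**Working it through.** The plan gives no figure on this point, so there is none to reproduce. The check has three parts.

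**1. When do the two orders of operation differ?** Let S and R be 1 when an episode is serious and when it is related. Merging first gives max(S) × max(R). Classifying first gives max(S × R). With k episodes of one PT there are 4^k ordered patterns. Merging first counts (2^k − 1)² of them; classifying first counts 4^k − 3^k.

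| Episodes k | Patterns | Merge first | Classify first | Over-count | Under-count |
|---|---|---|---|---|---|
| 1 | 4 | 1 | 1 | 0 | 0 |
| 2 | 16 | 9 | 7 | 2 | 0 |
| 3 | 64 | 49 | 37 | 12 | 0 |

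The two discordant patterns at k = 2 are serious-unrelated with non-serious-related, in either order. Merging first never loses a true serious reaction. Counts of all adverse events, all adverse reactions and all serious adverse events are the same under both orders, because each depends on one attribute at most. The table counts logical patterns, not frequencies.

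**2. How large could it be?** The documents do not say how often a PT recurs or how often assessments differ. The inputs here are assumptions: each episode serious with probability p = 0.1 to 0.2, related with probability q = 0.5 to 0.8, and 5 to 10 patients per 100 with one repeat pair. Seriousness and causality are taken as independent of each other. With between-episode correlations a (seriousness) and b (causality), the expected excess per pair is

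2 × p(1 − p)(1 − a) × q(1 − q)(1 − b).

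For a = b = 0 the lowest value is at p = 0.1, q = 0.8: 2 × 0.09 × 0.16 = 0.0288. The highest is at p = 0.2, q = 0.5: 2 × 0.16 × 0.25 = 0.0800. The table takes 5 pairs at the low value and 10 at the high one. The chance of at least one false record is 1 − (1 − excess)^pairs.

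| Correlation between episodes | Excess per pair | Expected per 100 patients | Chance of at least one |
|---|---|---|---|
| None | 0.0288–0.0800 | 0.14–0.80 | 14–57% |
| Causality 0.5 | 0.0144–0.0400 | 0.07–0.40 | 7–34% |
| Both 0.5 | 0.0072–0.0200 | 0.04–0.20 | 3–18% |
| Causality always agrees | 0 | 0 | 0% |

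The first row is the least plausible, since it lets causality vary freely between episodes of the same PT in the same patient on the same drug.

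**3. Does the SAP direct the merge-first reading?** Set side by side, the relevant places point the other way.

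- The section 10.2 rows for serious adverse events and adverse reactions classify on the values produced by AE matching. Those values are the input to the priority rules, not their result.
- The adverse reaction row defines the reaction first and only then says that repeats of a PT count once.
- Table 2.14 takes serious reactions as a subset of adverse reactions. Where a patient has several episodes of the same serious reaction, it counts the earliest. A record already merged to patient and PT has no episodes left to choose from.
- Naming AERELS for adverse reactions is harmless: any related episode makes the merged record related, so the all-reaction count is right in either order. AESERS is not named in that row, so nothing there tells the analyst to cross the two.

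**The case for a change.** The strongest case for a change is this. Sections 5.1.1 and 5.1.2 send the reader to the derivation chapter for definitions, and that chapter has no serious adverse reaction. The only seriousness and causality variables it names are the merged ones, both in A_AE_AL. The event-level wording permits classification first but does not demand it, and the reference to the definition document concerns how each variable is set, not how they are combined. One sentence would close the gap at almost no cost.

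The first part stands: the order of operations is not written down. It carries little weight, because both component terms are defined, Table 2.14 forms the third as a subset, and the wording leans towards the right order. The definition document may also settle the matter; it is not available here.

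The wider remedy is less attractive than it looks. Re-bracketing Table 2.2 would show causality as ruled out for a patient and PT for which another episode was judged related and is listed as a reaction in Tables 2.1 and 2.3. A rule by patient and PT does not fit Table 2.4, which counts patients per priority item. In Tables 2.5.5.X and 2.6, serious reactions appear only in parentheses in the counting notes, so it is unclear that such columns are planned.

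**Conclusion.** No change to the plan follows. The SAP leaves one order of operations unstated, and the natural reading of its definitions and of Table 2.14 is the correct one. Even on the other reading, the error runs only towards over-counting and hides no serious reaction, in keeping with the worst-case priorities that the SAP also uses for outcome. It touches only patients with at least two episodes of one PT that differ in both seriousness and causality in opposite directions.

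The size cannot be fixed from the documents. On the assumed inputs it is 0 to 0.80 records per 100 patients, probably below one. The conclusion rests on the analysts classifying episodes before counting by PT. The dataset definition document, if it said otherwise, would be the one thing that could alter it.
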